7.3 ALA STORAGE

ALA is provided in powder form in 10 g vials.

7.4 ALA PROCRUREMENT

Drug is supplied *gratis* by DUSA Pharmaceuticals, Inc. to our investigational pharmacy.

8.0 STATISTICAL CONSIDERATIONS

8.1 STATISTICAL ANALYSIS PLAN

Primary objective: We will assess 2 doses of 5-ALA, 10mg/kg and 20mg/kg, to determine the optimum ALA dose in terms of both sensitivity and specificity for residual tumor. The endpoint will be correspondence between intensity of *in vivo* fluorescence and PpIX concentration and the pathologist's quantification of tumor in biopsy specimens, e.g. percent tumor present. Receiver operating characteristic (ROC) curves will be calculated for each of the 2 combinations of ALA dose to estimate a level of fluorescence that distinguishes residual tumor from normal tissue with large true positive fraction (TPF) and small false positive fraction (FPF). A joint 95% confidence region for TPF FPF will be calculated, using $\alpha^*=1-\sqrt{1-\alpha}=0.975$ and univariate confidence limits for the individual probabilities. Having chosen the cut-points for each of the 4 combinations, positive and negative predictive values and diagnostic likelihood ratios will be calculated to describe the characteristics of each [18].

To compare the test characteristics of each ALA dose and to assess how the test characteristics are affected by demographic, disease, and surgical characteristics we will

fit multivariable generalized mixed models to tumor and normal biopsy specimens using robust standard errors to account for the correlation of samples taken from the same individual.

Secondary Objective: We will assess the correlation between the recorded *in vivo* qualitative assessment of fluorescence signal from the neurosurgeon with the post-surgical (i.e., *ex vivo*) absolute PpIX concentration detected in *ex vivo* tissue biopsies. The surgeon will subjectively score the intra-operatively observed fluorescence level as follows: 0, no fluorescence, 1, low fluorescence, 2, moderate fluorescence, or 3, high fluorescence [after 16]. We will first graph fluorescence against each PpIX concentration measurement (intraoperative and *ex vivo*) to evaluate the shape of the relationship. Additionally we will calculate a Spearman's correlation coefficient with 95% confidence interval to assess the correlation between fluorescence against each PpIX concentration measurement (intraoperative and *ex vivo*). The sensitivity and specificity of these observations will be determined [after 16], where the sensitivity of observable intraoperative PpIX fluorescence is the probability of observable intraoperative fluorescence given the presence of tumor cells in the tissue and specificity is the probability of no observable intraoperative fluorescence given that there are no tumor cells in the tissue [16]. We will also explore whether dose, patient, and disease characteristics affect the strength of the relationship between these measurements using multivariable generalized mixed models.

Tertiary Objective: To determine the association between the presence of fluorescence in the surgical cavity and the post-operative image enhancement on MRI. This includes the relationship between the amount and location of residual tumor detected by fluorescence, PpIX concentration, and intra-operative frameless stereotaxy following maximal resection versus the amount and location of tumor imaged post-operatively via CT and/or MRI. Assessment of agreement between fluorescence, intra-operative PpIX concentration, and MR intensity will be explored using the radiologist's assessment of MR intensity, measured on an ordinal scale. A multivariable ordinal logistic model will be fitted to assess the strength of the relationship and whether dose, patient or disease characteristics affect the relationship.

All models for all objectives will be fitted with robust standard errors to account for correlation between specimens taken from the same individual. Statistical models will be examined for goodness of fit; residual and influence statistics will be computed to ensure that outlying values do not have a disproportionate effect on the final models.

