2.2 PRIMARY OBJECTIVE

Primary objective: As a first step, we will assess 2 doses of 5-ALA, 10mg/kg and 20 mg/kg, to determine the optimum ALA dose in terms of both sensitivity and specificity for residual tumor. We will compare residual tumor detection by both *in vivo* qualitative and quantitative fluorescence imaging using histology of the biopsied tissue as the gold standard.

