4.4.2 LIGHT SENSITIVITY PRECAUTIONS

Before ALA administration, patients will be given verbal and written instructions for protection from sunlight by the staff surgeon or his delegate (see Section 4.7.1). It should be noted that these patients are hospitalized following surgery, so that there is in practice a very small possibility of their being exposed to bright sunlight outdoors. Nursing staff in the recovery room and on the ward will be instructed regarding the need to avoid accidental exposure to bright light in the first 24 hours.

4.4.3 .PATIENT GROUPS AND NUMBERS AND ALA DOSE

This clinical trial has ALA dose at 2 levels (10 and 20 mg/kg) and ALA administration time at 1 time point (3h). Consenting patients scheduled for surgery will be assigned to primary or recurrent arm based on clinical presentation, are then randomly assigned to one of two groups (for dose assignment) within each of the two arms of the study. Sample sizes of the 4 patient groups with two ALA dose levels are listed in the table below:

Table 3: Study Design and Sample Size

	Administration Time	
	3 hours New D _x	3 hours Recurrent D _x
10 mg/kg	30	30
20 mg/kg	30	30

For both patients with new and recurrent disease, biopsies will be taken at up to six sites identified by the surgeon: in the tumor center, tumor edge, area surrounding the tumor (if safe), areas seen to fluoresce intraoperatively and an area with MR enhancement outside

the tumor region (if this can be accomplished safely). Prior to collecting these biopsies readings will be taken at the biopsied location with the PpIX point probe by the surgeon. For each of the 6 biopsies, they will be divided into 3 parts and distributed for further analysis as follows: one portion will be sent to the pathologist for assessment of tumor percentage, one portion will be evaluated by the Division of Biophysics at the University of Toronto for PpIX concentration and the other for assessment of fluorescence.

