5.2 DATA ANALYSIS

5.2.1 FLUORESCENCE INTENSITY LEVELS VS. HISTOPATHOLOGY

The data sets will be collated into the 4 study groups (2 ALA doses and 2 study arms-- i.e., newly diagnosed and recurrent diagnosis) for analysis purposes.

Histopathology of the 1st part of the biopsies, performed by a single experienced neuropathologist (**i.e., [name]**) will be used as the gold standard. The white-light, fluorescence images, and intra-operative PpIX concentration readings will be compared to assess the sensitivity and specificity for biopsy-confirmed visible tumor.

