8.2 SAMPLE SIZE AND STATISTICAL POWER

Our study is powered appropriately for determination of the primary objective which involves the assessment of 2 doses of 5-ALA, 10mg/kg and 20mg/kg, to determine the optimum ALA dose in terms of both sensitivity and specificity for residual tumor. We calculate the total sample size for 80% power at the 0.05 significance level, given that the sensitivity will decrease by 15% with decreasing ALA dose within patient group (i.e. newly diagnosed or recurrent). Therefore our null hypothesis is that the sensitivity of the 10mg/kg dose is less than or equal to 15% different from the 20 mg/kg dose and the

alternative hypothesis is that the sensitivity of the 10mg/kg dose is greater than 15% different from the 20 mg/kg dose. We also take into account having multiple biopsies per individual on study. The total sample size per group per dose is as follows:

The primary objective of this Phase II study is to estimate and compare the combined diagnostic accuracy of in-vivo qualitative assessment of fluorescent signal in detecting residual tumor when used by the neurosurgeon using 2 doses of 5-ALA: 10 mg/kg and 20 mg/kg. The in-vivo qualitative assessment by the neurosurgeon will be coded on an ordinal scale ranging from 0 (no signal) to 3 (highest signal), as was done in a similar study reported by Roberts et al (J Neurosurg 2010 Apr 9, epub ahead of print) using a dose of 20 mg/kg in newly diagnosed gliomas. As in Roberts et al, we assume a score of 1 or higher will be considered positive. In the study by Roberts et al (2010) the reported sensitivity and specificity were 0.75 and 0.71, respectively, using the histopathologic reading as gold standard. In this study, because having high sensitivity and specificity are both important in terms of avoiding false negatives (which would involve not removing residual tissue) and false positives (removing normal tissue), the Youden index, defined as Sensitivity + Specificity -1 will be used as an overall measure of diagnostic accuracy. This study is designed so that if the dose levels of 10 and 20 mg/kg have true Youden indices that differ by 0.10 or more, then the probability is 80% or higher that the observed Youden index will be higher for the group with the higher actual index, i.e., the probability of selecting the correct dose level based on observed Youden indices will be 80% or higher.

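### Section 8.1 picks ROC cut-points and reports their accuracy on the same biopsies without correction, so each dose's absolute accuracy is optimistic on average; dose selection is spared if the fixed score rule in 8.2 governs it

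*Combined protocol and SAP*

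**What the plan says.** Under the primary objective, section 8.1 plans a set of ROC curves, "calculated for each of the 2 combinations of ALA dose to estimate a level of fluorescence that distinguishes residual tumor from normal tissue", aiming for a large true positive fraction (TPF) and a small false positive fraction (FPF). It plans a joint 95% region for TPF and FPF from univariate limits, with α* = 1−√(1−α) printed as 0.975. It then says: "Having chosen the cut-points for each of the 4 combinations, positive and negative predictive values and diagnostic likelihood ratios will be calculated".

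The quantitative markers belong to the primary objective. Section 2.2 compares detection by "qualitative and quantitative fluorescence imaging using histology of the biopsied tissue as the gold standard". The endpoint sentence in 8.1 names both fluorescence intensity and PpIX concentration. Section 5.2.1 adds that the images and "intra-operative PpIX concentration readings will be compared to assess the sensitivity and specificity for biopsy-confirmed visible tumor".

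On grouping, 8.1 refers first to 2 and then to 4 combinations. Section 5.2.1 says "The data sets will be collated into the 4 study groups", and Table 3 has four cells of 30 patients.

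Section 8.2 selects the dose differently. It uses the surgeon's 0–3 score, says "we assume a score of 1 or higher will be considered positive", and takes the dose with the higher observed Youden index (sensitivity + specificity − 1).

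The only model checks planned, at the end of 8.1, are goodness of fit, residuals and influence, with robust standard errors for biopsies from one patient.

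**The concern.** A cut chosen because it separates these biopsies well also fits their chance variation. Accuracy at that cut, measured on the same biopsies, overstates on average what the cut would do in new patients. Robust standard errors deal with clustering of biopsies within patients, and influence checks deal with outliers. Neither deals with the choice of the cut.

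At stake are the cut-points and the TPF, FPF, predictive values and likelihood ratios attached to them. A reader planning a later study, or looking for a PpIX threshold, could take them at face value.

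Predictive values have a further limit that no resampling removes. They depend on the share of biopsies that contain tumor, and "biopsies will be taken at up to six sites identified by the surgeon", so that share follows from surgical sampling.

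**Working it through.** **1. The plan's own figures (8.2).** Required n per group = Σp(1−p) × (1+2ρ)/3 × (0.8416/0.10)², summing over sensitivity and specificity at both doses. First row of the sample-size table: 0.1875 + 0.21 + 0.24 + 0.1875 = 0.825.
- ρ=0.10: 0.825 × 0.40 × 70.83 = 23.4 (plan: 23).
- ρ=0.20: 0.825 × 0.4667 × 70.83 = 27.3 (plan: 27).

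All 24 entries reproduce within 2 patients. At n=30 the probability of correct selection is 0.80–0.84. This calculation uses a cut fixed in advance, so it carries no cut-point optimism.

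**2. Optimism at a data-chosen cut (simulation).** From the documents: 3+3 biopsies per patient, 30 patients per dose and stratum or 60 per dose, within-patient correlation about 0.1–0.2, and Youden values from the sample-size table. Assumed: a binormal marker with equal variances, best true Youden mainly 0.35 or 0.45 (0.55 was also run for the maximum-Youden rule), and two candidate cut rules, since 8.1 names none. Optimism is the apparent Youden minus the true Youden at the same cut.

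| Cut rule | 30 per cut | 60 per cut |
|---|---|---|
| Maximum Youden | 0.051–0.066 | 0.033–0.043 |
| Closest to corner | 0.043–0.048 | 0.027–0.030 |
| 4-level score, cut chosen from data | 0.013–0.030 | 0.004–0.018 |

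For the maximum-Youden cut, the apparent value exceeded the true one in about 77–87% of simulated trials. So this is an average bias, not a certainty in a given trial.

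Example with 30 patients, best Youden 0.45 and maximum-Youden cut:
- Youden: apparent 0.49, true 0.435.
- TPF about 0.03 too high, FPF about 0.03 too low.
- Median positive likelihood ratio: about 2.9 apparent, 2.6 true.
- PPV 0.75 against 0.72; NPV 0.76 against 0.73.

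**3. Coverage of the joint 95% TPF/FPF region at the maximum-Youden cut, patient as cluster.** With Wald limits it is about 85% at 30 patients (84–88% over all settings) and 88–89% at 60 (up to 90%), against 92–95% when the cut is fixed. With logit-scale limits and a t quantile it is 92–94%.

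**4. Dose selection.** At 30 per dose, ρ=0.2 and Youden 0.45 against 0.35, correct selection is 79.8% with a fixed cut and 81.2% with cuts chosen from the data. The bias is similar in both doses: the mean observed difference is 0.094 instead of 0.099. With the best of three score cuts chosen per dose, correct selection is 83–84%, against 82% with the score ≥1 rule.

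**5. α\*.** 1−√0.95 = 0.0253, so each limit has confidence 0.9747, and 0.975² = 0.951. The printed 0.975 is therefore the per-interval confidence level. For p=0.75, n=30, ρ=0.2 the standard error is √(0.1875×1.4/90) = 0.054. The half-width is 2.236 × 0.054 = 0.121. With 0.975 entered literally as α, z = 0.031 and the half-width is 0.002.

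**6. Predictive values.** At TPF 0.75 and FPF 0.30, with 2, 3 or 4 tumor biopsies out of 6, PPV is 0.56, 0.71 and 0.83, and NPV is 0.85, 0.74 and 0.58. For example, with 3 of 6: 0.375/(0.375+0.15) = 0.71.

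**The case against.** Several counter-arguments have weight.

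- **Purpose.** The study is framed as a first step, fluorescence does not alter the resection (4.4.4), and 8.1 presents predictive values and likelihood ratios as descriptive. No section says the cut-points will be used elsewhere. This stands: the harm lies in how readers may use the results, and labelling alone would meet much of it.
- **Marker.** The ROC sentence speaks of a level of fluorescence. PpIX enters through the endpoint sentence and 5.2.1, and the secondary objective uses similar wording for the 0–3 score. If the score is meant, the optimism is small. This stands, and the range is given for both readings.
- **Group size.** If curves are drawn per dose, 60 patients inform each cut and the lower figures apply. The 4-group wording supports 30. The text does not settle it.
- **Coverage.** Section 8.1 does not name the type of limit. The marked shortfall belongs to Wald limits and is small with logit-t limits.
- **Gain from correction.** Total error falls only slightly, as shown under the fix.

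A reader might go further and infer that the choice between doses is biased. The documents do not support that: 8.2 compares observed Youden indices at a common pre-stated cut, and even data-chosen cuts hardly move the comparison. A reader might also infer that the joint region loses coverage through the α* error. It does not if 0.975 is used as a confidence level, which is the natural reading.

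**Conclusion.** The concern holds for the absolute accuracy of each dose at cut-points chosen from the data. For a continuous marker, mean optimism in Youden is about 0.04–0.07 with 30 patients per cut and 0.03–0.04 with 60, beside a design difference of 0.10. It is about 0.004–0.03 for the 0–3 score. These sizes rest on the assumed marker distribution, cut rule and 3+3 biopsies.

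Dose selection is not affected, on one condition: the score ≥1 rule must govern the primary comparison. Section 8.2 words that rule as an assumption and 8.1 does not repeat it.

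The α* value is a misprint to correct. The 2-versus-4 wording and the dependence of predictive values on sampling are minor. None of these three adds weight to the main point, which should be fixed but does not threaten the trial's design.

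**What to change.** 1. **Cut-points.** State the cut rule. Report TPF, FPF, Youden index, predictive values and likelihood ratios at data-chosen cuts from patient-level cross-validation (for example 10-fold repeated 5 times). Hold out whole patients and re-choose the cut in each fold. Show the uncorrected values beside them, labelled apparent. In simulation this left a bias in Youden of −0.002 to 0.000; a second, independent simulation agreed to within about 0.005. A bootstrap optimism correction removed less (0.453 against a true 0.435 at n=30).
2. **Intervals for the cross-validated values.** Use a patient-level bootstrap of the whole procedure, keeping all copies of a resampled patient in one fold. Coverage was 0.973–0.994, so somewhat conservative. Ordinary logit-t limits around cross-validated TPF and FPF covered only 0.82–0.87 jointly.
3. **Minimum alternative.** Label the cut-points exploratory and their accuracy apparent.
4. **Joint region.** Write α* = 0.0253, that is 97.47% limits for each of TPF and FPF. For the apparent region use the patient as cluster and logit-scale t limits.
5. **Wording in 8.1.** State that the dose comparison uses the score ≥1 rule of 8.2, use one number of groups, and note that predictive values apply only to the sampled mix of biopsies.

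The cost is SAP text and resampling code, with no extra data. Reported accuracy will be lower and noisier: the SD of the error in Youden rises from 0.069 to 0.085 at n=30 and from 0.051 to 0.060 at n=60. Total error improves little. At n=30, √(0.059² + 0.069²) = 0.091 uncorrected against 0.085 corrected; at n=60, 0.063 against 0.060. The benefit is mainly removal of bias.

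### Section 8.1 appears to compare the doses on the quantitative markers at cut-points chosen separately for each dose, so a gap in sensitivity or specificity may only reflect a different operating point on the same ROC curve

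*Combined protocol and SAP*

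**What the plan says.** The primary objective (2.2) covers both "qualitative and quantitative fluorescence imaging using histology of the biopsied tissue as the gold standard". The quantitative part is therefore primary, alongside the surgeon's score.

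For the primary objective, 8.1 sets out this sequence:

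- ROC "curves will be calculated for each of the 2 combinations of ALA dose to estimate a level of fluorescence" that separates tumor from normal tissue. The only guidance on choosing that level is that the true positive fraction should be large and the false positive fraction small.
- A joint 95% confidence region for the two fractions is calculated.
- "Having chosen the cut-points for each of the 4 combinations", predictive values and likelihood ratios are then computed as description. The count changes from two combinations to four within the paragraph, so cuts may be set per dose or per dose and stratum.
- "To compare the test characteristics of each ALA dose", and to study covariates, the plan will "fit multivariable generalized mixed models to tumor and normal biopsy specimens using robust standard errors" to handle correlation within a patient.

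The remainder of 8.1 adds no threshold common to both doses, no matched false positive fraction, no between-dose comparison of AUC or whole curves, and no allowance for cut-points being estimated from the data under analysis. The reference cited in that paragraph is a method for comparing ROC areas, but it is cited for predictive values and likelihood ratios, and its title limits it to curves from the same cases. Here the doses go to different randomized patients.

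For the surgeon's 0–3 score, 8.2 fixes the rule for both doses: "we assume a score of 1 or higher will be considered positive". It also adopts the Youden index as the overall accuracy measure.

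**The concern.** Sensitivity and specificity trade off along an ROC curve. If two doses have the same curve but their chosen cuts fall at different places on it, one dose looks more sensitive and the other more specific, although neither separates tumor from normal better.

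Empirical optimal cuts are unstable at this sample size, so such differences arise by chance. Robust standard errors allow for clustering of biopsies within a patient, but they treat the cut-points as if known in advance.

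This is a separate matter from optimism in each dose's own accuracy. Cross-validating within each dose would still leave the two doses at different operating points. What is at stake is whether a significant sensitivity or specificity contrast on the quantitative markers can be read as a dose effect.

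**Working it through.** **The plan's own figures.** The variance in 8.2 implies, for an 80% chance that the better dose shows the higher observed Youden index when the true indices differ by 0.10,

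n = (z₀.₈₀ / 0.10)² × Σp(1−p) × (1+2ρ)/3, with z₀.₈₀ = 0.8416,

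where the sum runs over both sensitivities and both specificities.

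- First row of the sample-size table: Σ = 0.1875 + 0.21 + 0.24 + 0.1875 = 0.825. Then n = 70.83 × 0.825 × 0.4 = 23.4 for ρ = 0.1 (plan: 23), and 70.83 × 0.825 × 0.4667 = 27.3 for ρ = 0.2 (plan: 27).
- Fifth row: Σ = 0.895, giving 29.6 for ρ = 0.2 (plan: 30).

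The other entries agree to within one patient. The sample size stands, and it does not involve a quantitative cut-point.

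**Simulation inputs**

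- From 8.2: 30 patients per dose within a stratum; three tumor-positive and three tumor-negative samples each; within-patient correlation 0.2; significance level 0.05 (two-sided assumed); reference sensitivity 0.75 and specificity 0.71.
- Assumed: an equal-variance binormal marker with separation d′ = z(0.75) + z(0.71) = 0.6745 + 0.5534 = 1.228, identical in both doses; correlation acting on the marker scale; the model outcome being the marker dichotomised at the chosen cut; and the cut rule, because 8.1 gives none.

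Each simulated trial picks the cuts, then tests the dose difference in sensitivity and in specificity with patient-level robust standard errors. There were 3000 trials per setting. The Monte Carlo standard error is about 0.8 points near 27% (√(0.277 × 0.723/3000)) and 0.4 points near 5%.

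**Rejection rates with identical ROC curves**

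| Cut-point rule | Sensitivity test | Specificity test | Either | Observed sensitivity gap over 15 points |
|---|---|---|---|---|
| Own Youden maximum per dose | 27.7% | 26.6% | 38.4% | 22.3% |
| Own closest-to-corner per dose | 6.6% | 6.2% | 11.9% | 4.6% |
| Own cut at specificity 0.71 or more | 10.3% | 0.0% | 10.3% | 7.5% |
| One Youden cut common to both doses | 5.5% | 5.2% | 10.2% | 3.5% |
| Cut fixed in advance | 5.7% | 5.8% | 11.1% | 4.3% |

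Two independent 5% tests would give 1 − 0.95² = 9.75% for either. In the third row the rule pins the observed specificity, so the specificity test cannot reject.

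**Sensitivity to assumptions (sensitivity test)**

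- Youden cuts: 30.4% at correlation 0.1 and 26.7% at 0.3.
- Closest-to-corner: 8.1% and 4.5% at the same correlations.
- Specificity 0.71 or more: 13.3% and 8.4%.
- Youden cuts, correlation 0.2, other ROC shapes: 39.2% at d′ = 0.8, 18.9% at 1.8, 13.9% at 2.5.
- One Youden cut per dose with both strata together (60 per dose): 33.7%. Four stratum-specific cuts, pooled for the test: 26.7%. More patients do not remove the effect.
- Logistic GEE with robust errors, closer to the planned model: 25.5% (400 trials).

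**Contrasts that do not reward a shift along the curve**

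- Youden index compared at each dose's own optimum: 3.5%.
- AUC difference with a clustered variance: 6.2%. With a patient-level jackknife in a near-identical setting (d′ = 1.1955): 5.3%.

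**Direction.** Under Youden cuts, about 26 of the 27 percentage points of false sensitivity gaps come with specificity moving the opposite way.

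**The case against.** The strongest reply is that 8.1 never says the mixed model takes results dichotomised at dose-specific cuts. The outcome could be the surgeon's score under its fixed rule, or the continuous marker modelled on tumor status and dose. A tumor-by-dose contrast on the continuous marker rejects in only 5–6% of null trials. This stands: the comparison at separate cuts is an inference from the order of steps (cuts, then test characteristics, then comparison), and the text leaves it open.

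Second, 8.2 makes the Youden index the overall measure and selects the dose on it. If Youden also governed the quantitative comparison, there would be no inflation. This also stands, but 8.2 applies the index to the surgeon's score, and 8.1 does not name it for the quantitative markers.

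Third, the false gaps are mostly visible trade-offs. With Youden cuts, a significant result on either test without an opposing shift in the other measure occurred in only about 1.6% of null trials, and 8.1 plans a joint region for the two fractions. This softens the point without removing it: the region is per dose, treats the cut as known, and is not the between-dose test.

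Fourth, a large true positive fraction with a small false positive fraction describes closest-to-corner at least as well as Youden, and there the rate is near nominal. This stands, and it is why no single rate should be quoted without its rule.

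**Conclusion.** The concern holds in a conditional form. On its natural reading, 8.1 compares sensitivity and specificity between doses at cuts chosen separately from the same data, with standard errors that omit the cut-point uncertainty. The false-positive rate per separate comparison then depends on a rule the plan does not state: about 27% with Youden-maximising cuts, about 6% with closest-to-corner, and roughly 5–39% over the rules and ROC shapes examined. All of this assumes identical binormal curves and the 8.2 inputs.

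Three stronger readings are tempting, and the documents do not support them.

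- A reader might infer that 27% is the plan's error rate. It belongs to one assumed cut rule and one assumed model outcome.
- A reader might infer that the plan will often declare the wrong dose a better discriminator. Nearly all the false sensitivity gaps under Youden cuts are trade-offs, and the Youden contrast at each dose's own optimum stays at 3–4%.
- A reader might infer that the trial's sizing is undermined. The sample size rests on the surgeon's score with a rule fixed for both doses.

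This is a cheap improvement that should be made to the quantitative half of the primary analysis. It does not call for a redesign.

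**What to change.** In 8.1, name the between-dose contrast for the quantitative markers as one of the following:

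- the difference in AUC, within the newly diagnosed and recurrent strata; or
- sensitivity at one pre-specified specificity common to both doses.

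Obtain the confidence interval from a bootstrap that resamples patients and re-derives any cut inside each resample. That last step matters: aligning observed specificity while treating the cut as known still gave 8–13% for sensitivity. A shared absolute threshold would restore the error rate only if both doses put the marker on the same scale, so it is not the preferred remedy.

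Report sensitivity and specificity at dose-specific cuts descriptively, as 8.1 already does for predictive values and likelihood ratios, and do not test them separately between doses. State the rule that selects those cuts, whether there are two or four of them, and the outcome of the mixed model.

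The cost is a few sentences in the SAP and a routine resampling program. One small downside is that AUC averages over specificities that would not be used clinically; the common-specificity option avoids this. The score-of-1-or-higher rule and the 8.2 sample size need no change.
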